DMC or DSMB charter
Data safety monitoring plan
Adverse event log
Investigator brochure or package insert for drugs
Instructions for use or approved FDA labeling for devices
Sponsor justification or FDA documentation for non-significant risk device study
IND or IDE documentation
Patient information sheet for Humanitarian Use Device
Approval order for Humanitarian Use Device
Product labeling for Humanitarian Use Device
HIPAA waiver
HIPAA authorization
Authorization to contact form
Consent form(s)
Assent forms(s)
Fact sheet(s)
Multi-site communication plan
Study staff training plan
SOPs or Manuals of Operations

INVESTIGATOR STUDY PLAN - REQUIRED

	Screening log
	Compensation log
	Certificates of translation or translator attestations
	Data use agreements, memoranda of understanding,
	Documentation of data/specimen anonymity (i.e., provider will never break the code)

## Crowdsourcing Study

**Study Design and Power Analysis:** The focus of this proposal is to assess which communication principles influence self-reported responses on source trust, psychological reactance, message liking, attitudes, and behavioral intentions of young adults. Eligible participants will complete an online consent and tobacco use questions on a Qualtrics survey before random assignment to one of four experimental conditions in a 2 (Source: expert and peer) X 2 (Presentation: one-sided and two-sided) design. For the crowdsourcing study of Aim 1, we wish to identify top-rated features to be tested further using psychophysiological testing. We investigated the stability of ranks as a function of number of participants, using simulated data (500 sets of simulated data per run) based on observed outcome distributions from Stevens et al. (2021). These runs indicated that ranks for the top 3 features are stable with 50 participants each receiving 18 messages. Separately for vapers and susceptible non-vapers, within each of 8 possible conditions (2 expert types x 2 peer types x 2 presentation types) we will recruit n=50 participants, or n=400 for each vaping status and n=800 total. Scores for each measure will be summed and averaged across all messages within each vaping status condition. I will use a multi-attribute decision-making (MADM) framework to produce a dataset containing data on participant response to each message with source + presentation type. I will merge crowdsourced and psychophysiological data to rank messages and determine optimal content.

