The proposed research is guided by biobehavioral theories of tobacco regulatory science,^{39,40} psychology,^{15,41} and communication.^{42,43} By using previously tested education messages,⁴⁴ we will determine an optimal combination of message source and presentation type to increase message acceptance and e-cigarette harm perceptions. We will compare the effects of two sources (expert and peer) and two message presentation types (one-sided and two-sided) for young adult vapers and susceptible non-vapers. We will use crowdsourcing (N=800) for post-test self-report measures (message acceptance, harm perceptions) to determine optimal messaging. The goal of this study is to determine optimal message source and presentation for young adult vapers and susceptible non-vapers to increase message acceptance and harm perceptions using crowdsourcing.

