12. DATA AND SPECIMEN BANKING*

We will not collect any information directly linked to the identity of individual subjects. It is possible that IP addresses may be collected. We will de-identify the dataset by removing IP addresses. The data will be stored in UMass Chan Medical School OneDrive indefinitely and will be accessible to the PI and the research coordinator. De-identified dataset will be available to other researchers upon request.

13. Data Analysis and Management*

Scores for each measure will be summed and averaged across all messages for each vaping status population. A multi-attribute decision-making MADM framework⁵⁴ will be used to produce a dataset containing data on participant response to each message with source + presentation type. Crowdsourced data will be merged with the Study part 2 data (psychophysiological testing) to rank messages and determine optimal message type.

Once the crowdsourced and psychophysiological data collection is complete, we will use the MADM framework⁵⁴ to determine the optimal combination of message source and presentation type. We will create a decision matrix in which each row represents a message type (source + presentation) and each column (attribute) represents a construct via the crowdsourced and

INVESTIGATOR STUDY PLAN - REQUIRED

psychophysiological studies. Each message type will receive an average score for each self-report (e.g., message acceptance, harm perceptions) and psychophysiological measure (e.g., heart rate, skin conductance, eye-tracking) for each vaping status. The overall rank for each message type will be calculated by taking the average of ranking scores of the crowdsourced and psychophysiological data across the measures within each message type. Each measure will be equally weighted, as a previous study using MADM has indicated no differences in ranks when weighting psychophysiological or self-report measures differently.⁵⁴ We will use statistical software (e.g., Stata, SPSS, R) to conduct analysis.

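### Is N=800 justified by a selection of top features that the protocol's ranking of all message types does not contain?

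*SAP*

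**What the plan says.** The SAP (Crowdsourcing Study) gives Part 1 a screening purpose: "we wish to identify top-rated features to be tested further using psychophysiological testing". The sample size rests on simulated data, 500 sets per run, from which the SAP concludes that "ranks for the top 3 features are stable with 50 participants each receiving 18 messages". It then sets the cells: "within each of 8 possible conditions (2 expert types x 2 peer types x 2 presentation types) we will recruit n=50 participants", giving 400 per vaping status and 800 in all. It closes by saying that the crowdsourced and psychophysiological data will be merged to "rank messages and determine optimal content".

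Protocol section 13 (Data Analysis and Management) places the ranking later: "Once the crowdsourced and psychophysiological data collection is complete". In its decision matrix "each row represents a message type (source + presentation"). "Each message type will receive an average score for each self-report" measure and for each psychophysiological measure, separately by vaping status, and the overall rank is the equally weighted average of the ranks. Protocol section 5 sets out the factors: "We will compare the effects of two sources (expert and peer) and two message presentation types (one-sided and two-sided"). Section 13 does not give a number of rows; four is inferred from this 2 × 2 design.

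**The concern.** Read together, the documents seem to describe two different decisions. The SAP sizes Part 1 to find a stable top three, apparently as a filter before Part 2. The protocol has no filter and needs a psychophysiological score for every message type. If a type were dropped after Part 1, its averaged rank could not be computed as section 13 requires, and the best type might be chosen from an incomplete field.

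The sizing also looks detached from Aim 1. That aim compares source and presentation between participants, while the simulation concerns *features*, a term the SAP does not define. No stability threshold, effect size, SD, alpha or power is given. A reader could reasonably ask what 800 participants deliver for the choice among four types.

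**Working it through.** **The plan's own figures.** Protocol Appendix A lists two expert and two peer directions, so the cells are (2 + 2) × 2 = 8. Then 8 × 50 = 400 per vaping status and 2 × 400 = 800. Both totals agree with the SAP. With four types, each has 400/4 = 100 participants per vaping status. The figure of 50 cannot be reproduced, because the inputs to the simulation are not given.

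**Would the matrix have empty rows?** This depends on what a feature is and on how many advance. The SAP gives neither. Suppose, as an assumption only, that exactly three advance:

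| Meaning of feature | Rows without a psychophysiological score |
|---|---|
| Message type | 1 of 4 |
| One of the 8 cells | 1 of 4 in 4 × 2³ = 32 of the C(8,3) = 56 triples; 2 of 4 in the other 24 |
| Factor level (expert, peer, one-sided, two-sided), type advances only if both its levels are chosen | 2 of 4 |
| Factor level, type advances if either of its levels is chosen | 0 of 4 |
| Individual message within each type | 0 of 4 |

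The fourth line holds because any three of the four levels include both levels of one factor, and so touch every type. The range is 0 to 2 empty rows, set wholly by assumptions that the documents do not make. The last line has textual support, since both documents speak of ranking messages.

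**Does a simulation at 50 per cell say anything about four types at 100?** An illustration with a normal model and 20,000 runs covers one self-report measure in one vaping status. A participant's mean over 18 messages has variance ICC + (1 − ICC)/18 in units of the single-rating variance: 0.3 + 0.7/18 = 0.339 at ICC 0.3, and 0.7 + 0.3/18 = 0.717 at ICC 0.7. Both the ICC (0.3 to 0.7) and the equal gaps between neighbouring ranks are assumed.

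| Gap (single-rating SD) | 8 cells, n=50: top 3 in right order | 4 types, n=100: full order right | 4 types, n=100: best type first |
|---|---|---|---|
| 0.05 | 0.07–0.16 | 0.19–0.30 | 0.56–0.68 |
| 0.1 | 0.26–0.45 | 0.45–0.68 | 0.78–0.88 |
| 0.2 | 0.66–0.87 | 0.86–0.98 | 0.95–0.99 |
| 0.3 | 0.89–0.99 | 0.98–1.00 | 0.99–1.00 |

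At the same gap and ICC, four types at 100 are ordered more reliably than the top three of eight cells at 50. With four types, a correct top-three order is also the full order. Averaging two cells into a type may narrow the gaps, so this comparison is a guide and not a proof.

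**Precision per vaping status**, in SDs of a participant's averaged score. SE = √(2/n); half-width = t × SE; detectable difference at 80% power and two-sided 0.05, unadjusted (these criteria are assumed):

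| Contrast | n per group | SE | 95% half-width | Detectable difference |
|---|---|---|---|---|
| Two cells | 50 | 0.200 | 0.40 | 0.57 |
| Two message types | 100 | 0.141 | 0.28 | 0.40 |
| Main effect of source or presentation | 200 | 0.100 | 0.20 | 0.28 |

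**Sub-type allocation.** The documents do not state how the two sub-types are split within a condition. If the split were left to chance, the binomial 95% range in 100 people is 40 to 60. The type mean would then move by at most |0.6 − 0.5| = 0.1 of the difference between sub-types.

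**The case for a change.** The best case for a change has two parts. First, the selection sentence in the SAP and section 13 of the protocol cannot both be followed if any type is left out of Part 2. That is true: dropping a type would leave its merged rank undefined. Second, the reading that removes this conflict, individual messages within each type, weakens the sizing. Source and presentation are constant within a cell, so ranking 18 messages among 50 people does not directly size a comparison between participants. That is also true, and on this reading the SAP gives no direct sizing for Aim 1.

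Neither part shows a wrong result. The SAP uses the top three as a benchmark of stability; it does not say that three units advance or that the rest are discarded. Section 13 states which scores each type must have, and an analyst who follows it will carry all types through. Rank stability is also a fitting criterion for a plan whose output is a ranking. Where a feature is a cell or a type, having 100 per type and not 50 is more information, not a mismatch. Finally, this protocol covers Part 1 only. How Part 2 chooses its stimuli and its sample size may be set out in documents not supplied here, so the absence of sizing for the merged ranking can be claimed only for these two documents.

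The SAP writes the eight cells as a product of expert types, peer types and presentations. This is loose notation: Appendix A makes the intended structure plain and the count is right.

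**Conclusion.** No change is needed. The documents leave *feature* undefined, do not say how many advance, and report no stability criterion. These are gaps in description that section 13 of the protocol lets an analyst fill sensibly: score every message type on both kinds of measure, then rank. Doing so alters no analysis and no number of participants.

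The possible harm runs from 0 to 2 of 4 rows unscored, and it arises only if units are dropped by a rule that neither document states. The sample size reproduces arithmetically. It gives 100 per type per vaping status, enough to detect about 0.40 SD between two types and 0.28 SD for a main effect under the assumed 80% power and two-sided 0.05. The documents set no required effect against which this could be judged too small.

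The conclusion rests on four inferred rows from the 2 × 2 design and on Part 2 testing every type, as section 13 requires. A Part 2 document that did drop whole types would reopen the question.
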